### **3.3. Sample Size and Power**

Eligible subjects will be randomized 1:1:1:1:1:1:1 to the study groups in a blinded fashion. There will be 25 subjects per study group. The total sample size will be 200 patients. Assuming a common standard deviation of 15 and an alpha of 0.05, enrolling a total of 25 in each group will have 90% power to detect an

average difference in percent change in LDL-C of 15 between rosuvastatin and each supplement.

#### **4. Study Analysis Sets**

##### **4.1. Full Analysis Set**

The full analysis set (FAS) consists of all enrolled patients. Efficacy variables will be analyzed based on the FAS as the primary population.

##### **4.2. Safety Analysis Set**

The safety analysis set (SAS) consists of all patients who received at least one dose of study medication/supplement. The safety population will be used for the analyses of safety variables.

##### **4.3. Per-protocol Analysis Set**

The per-protocol analysis set (PPAS) consists of all patients who received at least 80% of the prescribed study medication/supplement. Patients will be categorized by they study medication/supplement taken.

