4.3.4 Prohibited medication/supplement and therapies

New use of prescription medication/supplements for elevated cholesterol or triglycerides during participation in the trial.

New use of over the counter dietary supplements marketed for cholesterol health or triglyceride health for 4 weeks prior to or during participation in this study are prohibited. Chronic use of supplement types other than those being assessed in the trial will be permitted if doses have been stable for 4 weeks or longer.

Patients will be encouraged to maintain lifestyle habits present at the time of trial enrollment during the course of the trial. Significant dietary and physical activity modifications will be discouraged over the 4 weeks of participation. Participants are not to enroll in weight loss programs during the trial.

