4.4 Study group blinding

Subjects, investigator staff, persons performing the assessments, and the clinical trial team will be blinded to assigned study group. Baseline laboratory values will not be blinded to the subjects, investigator staff, and the clinical team. Additional lipid labs will be prohibited for the 4 week participation period. The Day 28 labs will not be blinded.

It is expected that the need for unblinding of a patient's study group will be extremely rare. Every effort should be made to preserve the blind unless there is a compelling reason that knowledge of the specific treatment would alter the medical care of the patient.

5 Informed consent procedures

Eligible subjects may only be included in the study after providing IRB approved informed consent. Informed consent must be obtained before conducting any study-specific procedures. Subjects will be prescreened using historical laboratory values within 13 months of screening prior to consenting. Subjects that screen fail will not be eligible for rescreening.

6 Visit schedule and assessments

Subjects should be seen for all visits/assessments as outlined in the assessment schedule. The baseline and final visits will be completed in-person or remotely.

The fasting lipid draw and complete metabolic panel (CMP) at Day 0 and Day 28 must be obtained from a Cleveland Clinic lab. Recently acquired lipid labs and complete metabolic panel may be used in place of a Day 0 lab draw if acquired within 4 weeks of screening at a Cleveland Clinic lab and performed in the fasting state. Subjects are to remain on study medication/supplement until Day 28 labs are drawn.

Study personnel will use the following historical information to input into the ASCVD risk calculator to determine eligibility:

- Age
- Gender
- Race
- Systolic blood pressure
- Diastolic blood pressure
- Treatment for high blood pressure and diabetes
- Current smoking status

If a historical blood pressure is not found within 1 year of screening, patient reported is acceptable.

Lipid panel, hs-CRP will be collected at the initial visit and Day 28.

- Lipids: Indirect **LDL-C** (Total Cholesterol, HDL-C, and Triglycerides)
- Inflammatory markers: **hs-CRP**

Table 7-1 Assessment Schedule

Activity	Study Day	
	Day 0 ^b	Day 28 ^{b,f} +4/-4 days
Informed consent obtained ^b	X	
Demographics	X	
Medical history	X	
Eligibility confirmed & subject randomized ^h	X	
Body weight ^g	X	
Height ^g	X	
Concomitant Medication/supplements	X	X

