#### **6.4. Study medication/supplement adherence**

Study medication/supplement adherence will be determined by the pill count returned, the pill count dispensed, and the amount of pills that are expected to be taken:

$$\frac{(\text{Number of pills dispensed} - \text{number of pills returned})}{(\text{number of pills indicated per day per study medication/supplement} * \text{number of days of follow-up}^\dagger)}$$

The number of pills expected to be taken through day 28 days will vary for each medication/supplement (Appendix A). The expected amount per day will be multiplied by the number of days of follow-up to get the total number of pill expected by the end of the study period.

Study medication/supplement adherence is defined as patients consuming at least 80% of the expected amount.

†The range of follow-up is 24-32 days. Only patients with at least 24 days of follow-up will be included in the study medication/supplement adherence calculation.

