### **7.6. Prior and Concomitant Medications**

A predetermined list of medications will be summarized at baseline, day 28 and any unscheduled visit. Prior or concomitant medication/supplements will be summarized for the safety set in separate tabulations based on a predetermined list of medication/supplements. Prior medication/supplement are defined as any medication/supplement a subject was taking prior to randomization in the study. Concomitant medication/supplements will include any medication/supplements taken during the study period. They include the following:

- ACE-Inhibitors
- Anticoagulants
- Angiotensin II Receptor Blockers (ARBs)
- Aspirin
- Beta Blockers
- Calcium Channel Blockers
- Diuretics
- Nitrates
- Thyroid medications
- Vitamin D
- Diabetic medications (insulin, oral meds)

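### The per-protocol set is defined by amount of product taken alone, so a patient who adds prohibited lipid therapy stays in the only planned sensitivity analysis of the primary endpoint

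*SAP*

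**What the plan says.** SAP 4.3 gives the only definition of the per-protocol set; Protocol 10.1 defines only the full analysis set and the safety set. The set "consists of all patients who received at least 80% of the prescribed study medication/supplement". A second sentence deals with grouping: "Patients will be categorized by they study medication/supplement taken".

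The 80% has one measure in the SAP, in section 6.4: pills dispensed less pills returned, set against the number due over follow-up. The same section adds: "Only patients with at least 24 days of follow-up will be included in the study medication/supplement adherence calculation".

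Protocol 4.3.4 sets two prohibitions on other lipid treatment. The first is "New use of prescription medication/supplements for elevated cholesterol or triglycerides during participation in the trial". The second is "New use of over the counter dietary supplements marketed for cholesterol health or triglyceride health", from four weeks before the trial until its end. Long-standing, stable use of supplement types not under study is allowed.

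On reporting, SAP 7.6 says: "A predetermined list of medications will be summarized at baseline, day 28 and any unscheduled visit". The list that follows has 11 entries: cardiovascular and blood-pressure classes, aspirin, anticoagulants, thyroid drugs, vitamin D and diabetes drugs. SAP 7.1 separately promises a table of major protocol deviations. SAP 8.1 and 8.2 use the per-protocol set for sensitivity analyses of the primary and secondary endpoints.

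**The concern.** The prohibited treatments are those marketed or prescribed to change the lipids that the trial measures. A per-protocol analysis is normally read as the result in patients who kept to the regimen. Here, a fish-oil patient who takes every soft gel and starts a statin on Day 7 counts as a per-protocol fish-oil patient. Protocol 3.1 says that LDL-C on rosuvastatin 5 mg settles within two weeks, so on the protocol's own reasoning an early start of a similar agent could act fully by Day 28.

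The stake is interpretive. SAP 8.1 tests seven comparisons in a fixed order, and the first one missed makes all later ones exploratory. If a comparison were missed, a reader would look to the per-protocol result to ask whether other lipid treatment had diluted the contrast. As defined, that set cannot answer, and the planned concomitant-therapy tables may not show whether the question arises.

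**Working it through.** **Step 1. The texts side by side**

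- *Membership:* at least 80% of the prescribed product (SAP 4.3), by pill count, with at least 24 days of follow-up (SAP 6.4). The follow-up condition removes short-stay patients but does not touch users of other lipid treatment.
- *Grouping:* by product taken (SAP 4.3). This can relabel a patient but excludes no one, and it gives no rule for a patient who took two studied products.
- *Link from the prohibition to the set:* none found in the Protocol or the SAP.
- *Tabulation:* of the 11 entries in SAP 7.6, none is a lipid or triglyceride drug, a studied supplement or another cholesterol supplement.
- *Other route to visibility:* the major-deviation table (SAP 7.1). The term major is undefined, and the table is not tied to the per-protocol set.

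**Step 2. The plan's own power figure (background)**

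Inputs from SAP 3.3 and 8.1: 25 per arm, SD 15, difference 15, two-sided alpha 0.05.

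- Standard error of a difference = 15 × √(2/25) = 4.243, and 15 / 4.243 = 3.536.
- Normal approximation: Φ(3.536 − 1.960) = 94.2%. Noncentral t with 48 df: 93.4%.

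The stated 90% is slightly conservative. By the t calculation, 22 evaluable patients per arm give 90.0%. This does not bear on the point.

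**Step 3. Illustrative size**

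The documents give neither a violation rate nor the effect of an added agent, so both are assumed. Let k patients in a 25-patient comparator arm each have an added LDL-C fall of e percentage points. The shift in that arm's mean is k × e / 25. Power uses the normal approximation with true difference 15 − shift and SD kept at 15.

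| k | e | Shift (points) | Share of 15 | Power |
|---|---|---|---|---|
| 0 | – | 0 | 0% | 94.2% |
| 1 | 20 | 0.8 | 5% | 91.7% |
| 1 | 30 | 1.2 | 8% | 90.2% |
| 1 | 40 | 1.6 | 11% | 88.5% |
| 3 | 20 | 2.4 | 16% | 84.4% |
| 3 | 30 | 3.6 | 24% | 76.6% |
| 3 | 40 | 4.8 | 32% | 67.2% |

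Example, k = 3 and e = 30: 3 × 30 / 25 = 3.6; 15 − 3.6 = 11.4; 11.4 / 4.243 = 2.687; Φ(2.687 − 1.960) = 76.6%. Mixing treated and untreated patients also widens the comparator SD, to √(225 + 0.12 × 0.88 × 900) = 17.9. The pooled SD is then √((225 + 320.04)/2) = 16.5, and the t calculation gives 66.7%.

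**Step 4. Direction**

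If k_c comparator patients and k_r rosuvastatin patients add an agent of the same effect, the net shift in the contrast is (k_c − k_r) × e / 25. It is zero if the counts are equal and reverses if the rosuvastatin arm has more. The table covers the case k_r = 0.

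**The case against.** - **The set does what SAP 8.1 says.** Its stated aim is the result in patients who took the prescribed quantity, which makes it an adherence analysis. This stands in part: the 80% rule fits that aim. But the set is named per-protocol, it is the only sensitivity analysis of the primary endpoint, and a patient on a prohibited lipid agent does not show the effect of the assigned product at any level of adherence.
- **Breaches are not hidden.** The major-deviation table may show them, SAP 7.6 defines concomitant therapy as anything taken, and its list could be read as open-ended. This stands as a limit. A reader might infer that violators vanish from every table; the documents do not support that. They could appear as deviations, and in the concomitant tables for any listed drug. What is missing is a planned row for the prohibited agent itself.
- **Unequal breaches between arms are not shown.** Protocol 4.4 says "Baseline laboratory values will not be blinded to the subjects, investigator staff, and the clinical team", and a reader might infer that patients on placebo or an ineffective supplement will see no benefit and add treatment more often. That inference fails: baseline values are known in all eight arms, subjects are blinded to group, and further lipid tests are prohibited during the four weeks. A patient may suspect lack of effect but, under the protocol, has no on-treatment result to confirm it.
- **The violator count is invented.** Correct. Only the arithmetic can be checked, and four weeks is short.
- **A stricter rule may clash with grouping by product taken, and the eCRF may lack the detail.** Both stand and are dealt with in the fix.

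**Conclusion.** The gap is real and follows from the text: the membership rule ignores the lipid-therapy prohibition, and the concomitant-therapy list has no row for the agents concerned. Its size cannot be estimated from the documents. Under the assumed 20 to 40 point added fall, each violator moves a 25-patient comparator mean by 0.8 to 1.6 points toward rosuvastatin. The power figures are illustrations for hypothetical counts, not a forecast, and the true count may be zero.

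A reader might infer that the primary result is compromised. The documents do not support this. Primary inference rests on the full analysis set, which keeps all enrolled patients by design, and dilution from comparator-arm violators runs toward no difference, so it could not manufacture an advantage for rosuvastatin. The point concerns what the supporting analysis can tell the reader. It is worth correcting because the correction is small.

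**What to change.** **SAP 4.3.** Define the per-protocol set as patients who took at least 80% of the product and have no recorded use, between first dose and the Day 28 draw, of a treatment prohibited in Protocol 4.3.4 or of a second studied supplement. Stable use that Protocol 4.3.4 allows is not a reason for exclusion.

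**Reconcile with the grouping sentence.** A patient who took only a different study product is grouped under that product. A patient who took two studied products is excluded.

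**Timing.** Fix the list of exclusions before unblinding.

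**SAP 7.6.** Add rows by arm for prescription lipid or triglyceride drugs, for non-study use of each of the six studied supplements, and for other over-the-counter cholesterol or triglyceride supplements.

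**Cost.** The change is mainly SAP wording. The assessment schedule already records concomitant products at Day 0 and Day 28, so no visit or sample is added. The per-protocol set may lose a few patients. One check is needed: Protocol 4.3.3 speaks of recording the classification of prior products, so the sponsor should confirm that the eCRF identifies the individual agents and whether they were used after first dose. The full-analysis-set primary analysis stays as it is. If no one breaches the prohibition, the new exclusion removes no one and the added rows show that.

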#### **5. General Data Considerations**

Continuous variables will be summarized in terms of the number of observations (n), mean, standard deviation (SD), median, Q1 (25th percentile), Q3 (75th percentile), minimum and maximum. Other descriptive statistics (e.g. geometric mean) may be reported when appropriate.

Categorical variables will be summarized using frequency counts and percentages. Analyses that use other descriptive statistics will be identified with the analysis in the applicable SAP section.

SAS version 9.4 or higher will be used to perform all analyses and to generate output.

#### **6. Data Handling**

All data will be exported from the REDCap Cloud database. Randomization data will also be exported from the REDCap Cloud database. Assigned study medication will be blinded to study personnel. A general description of how the data will be handled is outlined below however, it may not encompass all that is found at the time of the analysis.

##### **6.1. Missing data**

Missing data will not be imputed unless otherwise specified. Only observed data will be used in the summaries and analyses.

## **6.2. Incomplete dates**

If a day or month is recorded as missing, it will be replaced by the first day of the month or January, respectively, provided this does not contradict any other dates recorded.

## **6.3. Data Definitions**

The following sections provide a general description of the derived variables for data analyses.

### **6.3.1. Study Day**

#### **6.3.1.1. Fasting lipid panel**

The fasting lipid draw and complete metabolic panel (CMP) at Day 0 and Day 28 must be obtained from a Cleveland Clinic lab. Recently acquired lipid labs and complete metabolic panel may be used in place of a Day 0 lab draw if acquired within 4 weeks of screening at a Cleveland Clinic lab and performed in the fasting state.

#### **6.3.1.2. Study Medication**

Day 1 of the study is the first day that subjects start study medication/supplement.

#### **6.3.1.3. Body Weight**

Historical documented height and weight may be used. Weight to be within the last 3 months. Subject reported is acceptable.

### **6.3.2. Baseline laboratory values**

Baseline is defined as the Day 0 lab draw. Recently acquired lipid labs and CMP may be used in place of a Day 0 lab draw if acquired within 4 weeks of screening at a Cleveland Clinic lab and performed in the fasting state

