4.1 Inclusion criteria

Subjects eligible for inclusion in this study must meet **all** of the following criteria:

1. Written informed consent must be obtained before any assessment is performed.
2. U.S. adults with primary hypercholesterolemia, 40-75 years of age.
3. Not currently taking statins or one of the dietary supplements included in the trial. Patients willing to discontinue a prohibited supplement for 4 weeks prior to enrollment will be allowed to participate.
4. LDL-cholesterol between 70 and 189 mg/dL.
5. Patients without diabetes mellitus and a 10-year risk of ASCVD between 5 and <20% using the pooled cohort risk equation. *

Or

Patients with diabetes mellitus in females 50-60 years of age or males 40-50 years of age with an LDL-C between 70-189 mg/dL and with an ASCVD risk below 20%.

*<http://tools.acc.org/ASCVD-Risk-Estimator-Plus/#!/calculate/estimate/>

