4.3.5 Study group assignment, randomization

Randomization will occur using REDCap Cloud electronic database platform. Study medication/supplement will be dispensed by the investigational pharmacy in a blinded fashion for in person visits to study personnel or shipped to the subjects by the investigational pharmacy following randomization. Day 1 of the study is the first day that subjects start study medication/supplement. In the event that study medication/supplement is shipped to subjects, study personnel will verify the start of study medication/supplement (Day1) for medication/supplement accountability.

The study medication/supplement will be supplied from commercially available products and administered according to the package insert. The rosuvastatin 5mg and placebo will be provided by Astra Zeneca. The over the counter supplements will be purchased and due to documented history of supplement tainting, supplements may be tested for unlabeled enhancing impurities retrospectively if deemed necessary per data findings. If we observe > 15% lowering in LDL cholesterol, we will test for impurities.

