Hs-CRP	X	X
CMP, LDL-C, TC, HDL-C, and TG ^{c,d}	X	X
Pregnancy test ^a	X	
Study medication/supplement dispensed ⁱ	X	
Adverse events		X
Study medication/supplement adherence ^e		X

^a Females of child-bearing potential only, urine or serum at investigator's discretion.

^b The baseline (0) and 28 Day visit may be completed remotely. Consent will be obtained prior to completion of the baseline visit and may be completed remotely in accordance with Cleveland Clinic guidelines

^c Fasting lipid panel and complete metabolic panel should be drawn at a Cleveland Clinic lab facility. Patients should fast for approximately 8 hours.

^d Recently acquired lipid and complete metabolic panel labs may be used in place of a Day 0 lab draw if acquired within 4 weeks of screening at a Cleveland Clinic lab.

^e Study medication/supplement adherence will be assessed with a pill count. The bottle will be returned to the study site to retain until the end of study.

^f If enrolled for over 14 days and the patient discontinues study medication/supplement perform Day 28 lab work (ITT principle).

^g Historical documented height and weight may be used. Weight to be within the last 3 months. Subject reported is acceptable.

^h Randomization and eligibility confirmation may occur on different days from baseline pending lab results

ⁱ Study medication/supplement will be dispensed by the investigational pharmacy for in person visits to study personnel or shipped to the subjects by the investigational pharmacy following randomization.

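### Baseline LDL-C may be a panel from up to 4 weeks before screening, with no requirement that it follow the supplement washout, although blood must be drawn at Day 0 for hs-CRP in any case

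*SAP*

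**What the plan says.** SAP 6.3.2 starts from a simple rule, "Baseline is defined as the Day 0 lab draw", and then relaxes it: "Recently acquired lipid labs and CMP may be used in place of a Day 0 lab draw if acquired within 4 weeks of screening". The substitute must be a fasting sample from the sponsor's own laboratory. SAP 6.3.1.1, Protocol section 6 and footnote d of Protocol Table 7-1 carry the same allowance, though footnote d itself omits the fasting condition. The window is counted from screening, not from randomization, Day 1 or the end of washout.

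SAP 6.3.3 makes this value the denominator of percent change, and SAP 8.1 makes it a covariate in every primary model.

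Protocol 4.1, criterion 3, admits former users of the trial products: "Patients willing to discontinue a prohibited supplement for 4 weeks prior to enrollment will be allowed to participate". Exclusion criterion 8 sets the same 4 weeks before participation.

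The allowance covers lipids and the metabolic panel only. In Table 7-1 the hs-CRP row is marked at Day 0 and Day 28 without footnote d, and Protocol section 6 says: "Lipid panel, hs-CRP will be collected at the initial visit and Day 28".

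Protocol 4.3.5 and SAP 3.1 attach a consequence to observed lowering: "If we observe > 15% lowering in LDL cholesterol, we will test for impurities".

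**The concern.** The washout is there so that a former user's LDL-C no longer reflects the stopped product when the trial starts. A baseline drawn before the product's effect has gone defeats that purpose for the one measurement on which the primary endpoint depends. If the product had lowered LDL-C, the baseline is too low. LDL-C then rises for reasons unrelated to the assigned arm, and the computed percent change understates lowering.

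Two things are at stake. A mixture of affected and unaffected participants widens the spread of percent change, which costs precision in each comparison with rosuvastatin. Each arm's own mean change also moves towards less lowering, and that matters if the impurity trigger is judged on an arm's mean. The concession buys little in return, because a Day 0 blood sample is needed for hs-CRP anyway.

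**Working it through.** **Timing.** Take enrollment as day 0, so washout runs from day -28 to day 0. Let screening come g days before enrollment. The oldest permitted panel is then at day -(28+g).

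- g = 0: day -28 at the earliest, so the panel lies within the washout window.
- g = 14: day -42, up to 14 days before washout starts.
- g = 28: day -56, up to 28 days before washout starts.

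The documents set no maximum for g. With follow-up of up to 32 days (SAP 6.4), the longest interval from baseline to final sample is at least 28 + 32 = 60 days, plus any gap between screening and start. With a Day 0 draw it is about 32 days, plus any gap between Day 0 and Day 1.

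**The plan's power figure.** Inputs from SAP 3.3 and 8.1: SD 15, difference 15 points, 25 per group, two-sided alpha 0.05. The noncentrality is 15 / (15 × √(2/25)) = 3.54 on 48 degrees of freedom. The two-sample t test then has 93.4% power; 23 per group is the smallest size that reaches 90%. The stated 90% is met with a little to spare.

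**Effect of a lowered baseline.** Let c be the true proportional change and d the proportion by which the stopped product had lowered baseline, with its effect gone by Day 28. The observed change is (1+c)/(1-d) - 1, so

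shift = (1+c) × d/(1-d).

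The shift is smaller where real lowering is larger. The illustration takes c = 0 in the comparator and c = -15% in the rosuvastatin arm, matching the planned difference. With a share p affected in each arm:

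- arm mean moves by p × shift
- arm SD = √(15² + p(1-p) × shift²)
- expected difference = 15 + p × (comparator shift - rosuvastatin shift)
- power uses the square root of the average of the two arm variances.

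The values of p and d are assumptions. The documents give neither.

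| p, d | Shift, comparator / rosuvastatin | Arm mean moves by | Arm SDs | Expected difference | Power |
|---|---|---|---|---|---|
| none | 0 / 0 | 0 / 0 | 15.0 / 15.0 | 15.0 | 93.4% |
| 5%, 10% | 11.1 / 9.4 | 0.6 / 0.5 | 15.2 / 15.1 | 15.1 | 93.1% |
| 10%, 15% | 17.6 / 15.0 | 1.8 / 1.5 | 15.9 / 15.7 | 15.3 | 91.8% |
| 20%, 20% | 25.0 / 21.2 | 5.0 / 4.2 | 18.0 / 17.2 | 15.8 | 87.1% |

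Worked for the third row: 100 × 0.15/0.85 = 17.65, and 0.85 × 17.65 = 15.0. The variances are 225 + 0.09 × 17.65² = 253.0 and 225 + 0.09 × 15.0² = 245.2, whose average gives a pooled SD of 15.78. The difference is 15 + 0.1 × 2.65 = 15.26.

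**Within-arm reading.** An arm whose true mean lowering is 15% has the shift in the rosuvastatin column. It would show 15 - 0.47 = 14.5%, 15 - 1.5 = 13.5% or 15 - 4.25 = 10.75% in the three scenarios.

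The power figures leave out adjustment for baseline LDL-C and age. Adding it needs a baseline distribution that the documents do not give, and the covariate would itself be the affected value.

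**The case against.** The other side has several good points.

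- **The allowance looks deliberate.** It appears in both documents and suits a trial with remote visits. That stands, but a remote visit does not remove the hs-CRP sample.
- **Few people may be affected.** A participant must have used a trial supplement, stopped it to join, supplied a substitute panel, had that panel drawn before the effect wore off, and used a product with a real LDL-C effect. This stands. Protocol 1.1 says about one third of US adults told they have elevated cholesterol use a supplement instead of a statin. That makes former users foreseeable, but it does not estimate this share. A 15-20% drop is also towards the high end for a plan that treats lowering above 15% as grounds for impurity testing.
- **The primary comparison is randomized.** This stands. A reader might infer that the rosuvastatin comparisons are biased, but affected participants are balanced across arms in expectation. In the illustration the expected difference moves by less than 1 point.
- **The impurity trigger is not a confirmatory endpoint.** It is also not defined as per arm, per person or against placebo, so the bias argument applies only to a within-arm reading.

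A reader might also infer that baselines will routinely be taken while people are still on a supplement. The documents do not support that. Table 7-1 places consent, eligibility and randomization at Day 0 and shows no separate screening visit. If screening and enrollment coincide, the panel falls inside washout. Footnote h lets randomization follow baseline on a later day, but while laboratory results are awaited, which fits a fresh draw better than a panel already in hand. A baseline from before washout needs screening to precede enrollment, which the text permits but does not describe.

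**Conclusion.** The point holds as a gap in the baseline rule. A substitute panel may fall during washout, or before it when screening comes earlier than enrollment, and nothing in either document prevents this. The consequence is added noise in the randomized comparisons and possible bias towards less lowering in within-arm changes, confined to former users of a lipid-active product who supplied a substitute panel.

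The size is not known. Under assumed inputs, power for a single comparison is about 93%, 92% or 87%, against 93.4% without the problem. Only the most extreme of these falls below the planned 90%, and all are before covariate adjustment. A reader might apply the full comparator shift to both arms and obtain 82.2% in the extreme case. That overstates the loss, because the shift shrinks in an arm with real lowering. The documents do not support a claim that the trial is underpowered or that its primary comparisons are invalid. The case for change rests on how little it costs.

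**What to change.** Draw the fasting lipid panel at Day 0 with the hs-CRP sample that is already required, and use it as baseline for every participant. Keep recent panels for eligibility only. This relies on washout being complete by Day 0, which follows if Day 0 is the day of enrollment; the text should say so.

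At the least, accept a substitute panel only if it was drawn after the full washout.

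The edits belong in Protocol section 6, Table 7-1 footnote d, SAP 6.3.1.1 and SAP 6.3.2. All four are needed, or the documents will contradict each other. Sample size, alpha and number of visits do not change. The cost is one extra lipid panel for some participants, at a blood draw that already takes place.
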